## **Protocol Title: Trial to Improve Multisensory Neural Processing, Language & Motor Outcomes in Preterm Infants**

---

IIA or above, culture documented sepsis or meningitis, moderate or severe bronchopulmonary dysplasia per modified Shennan definition), cumulative caffeine exposure post intervention, total parental skin-to-skin time during the study period and pretreatment status on the General Movements Assessment (GMA).

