## **Protocol Title: Trial to Improve Multisensory Neural Processing, Language & Motor Outcomes in Preterm Infants**

---

language intervention and that preterm infants exposed to STS care have increased multisensory processing efficiency compared to those who do not.

We have now designed a prospective, interventional RCT in preterm infants aimed at restoring more typical multisensory, rather than the unisensory, processing measures that were the outcomes of our pilot studies.

Our multisensory intervention using parents' voice and nurturing touch can be administered regularly in the NICU during sensitive periods of sensory development, even when parents cannot always be present. Our test of this multisensory intervention will involve 23 sessions of standardized, therapist-administered, auditory-tactile stimulation. This treatment will combine contingent presentation of recorded mother's voice delivered using a suck-activated system during holding with supportive tactile containment against the therapist's chest. This treatment will be tested in an internally-valid RCT. In addition to testing the efficacy of the treatment on gold-standard measures of language and motor functioning, we will also test whether the treatment effect is due to intermediate treatment effects on multisensory and unisensory processing. Understanding the mechanism by which the treatment works is important for laying the foundations of future improvements and potential recommendations for treatment that might be useful for wide-spread use even in lower resource settings with the ultimate goal of improving neurodevelopmental outcomes for these premature infants.

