### **Study procedures**

For infants who meet inclusion criteria at 31 weeks, consent is obtained and parent's voice is recorded and parent-scented T-shirt may be collected when possible. Study staff may approach parents of eligible infants about the study and obtain consent slightly before the infant is 31 weeks, however, other study procedures will not start until the infant reaches 31 weeks. Infants are then randomized to the control or intervention group. If a patient is randomized to the control group, parents will be given the opportunity to consent to the secondary part of the study if they are interested. This part of the study is observational only and does not influence randomization. ERP testing is performed prior to the intervention. Infants assigned to the MS group receive the standardized MS intervention over 2 weeks, starting at 32 0/7 weeks PMA or at enrollment prior to 36 weeks. For both control and intervention groups, standard care includes skin-to-skin care on parent, when present, and playing of parents' voice non-contingent on infant suck. Parents may be asked to complete the Baby Care Questionnaire (BCQ) during infant's stay in the NICU or as soon as possible after discharge. Prior to the infant's discharge, a brief neurological examination (HNNE) and motor assessment (GMA) may be completed. ERP is repeated after intervention is completed, which occurs at 36 weeks PMA on average.

All infants are seen at the NICU Follow-Up Program clinics at 3-4, 9-12 (Year 1) and 22-26 months (Year 2). At the 3-4 month visit, study staff may obtain the Baby Care Questionnaire (BCQ), a brief neurological exam (HINE), and a brief motor assessment (GMA). At the Year 1 visit, study staff may obtain the BCQ, Infant Toddler Sensory Profile (ITSP), HINE, GMA, Bayley III, and the Parenting Styles and Dimensions Questionnaire (PSDQ). At Year 2, study staff may obtain the the Bayley III, HINE, BCQ, CBCL, PSDQ, and PLS-5.

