### **Randomization**

Random assignment to groups will be carried out using unified reproducible methods (i.e. saved random number seeds) provided by our Biostatistics core. We will try to conceal allocation from all study personnel who could influence scores. Except for parent reports, examiners will be blind to treatment assignment. We will obtain recorded parent's voice from both groups with the intent of masking parents to assignment. Although we cannot fully mask parents to group allocation, as bedside nurses communicate regularly with them, we will address the potential effect on the parent questionnaire at one-year by deemphasizing the sensory nature of the outcomes to both groups, and instead focusing on the proven positive links between parental involvement and improved intersubjectivity.

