*Covariates:* Biological variables are factored into our research design as potential covariates. Several pretreatment covariates will be statistically controlled if needed. These variables will be quantified at the pretreatment period, as past research or theory suggests they may be associated with neurodevelopmental outcomes or sensory processing. If preliminary tests of between-group differences of these pretreatment variables and the pretreatment variables showing between-group differences are associated with putative mediators or neurodevelopmental outcomes, these will be statistical controlled. Their statistical interaction with treatment group must be tested as part of the process of determining whether they should be statistically controlled. Thus, the possibility that treatment varies as a function of these biological variables will also be explored. These include: gestational age at birth, sex, presence of severe white neural injury on neuroimaging (intraventricular hemorrhage grade III or IV, periventricular leukomalacia, cerebellar hemorrhage, ischemic or thrombotic injury), presence of systemic inflammatory conditions (history of necrotizing enterocolitis Bells Stage

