### **Analysis Plan**

#### **Power/Sample Size**

A total sample size of 230 (115 in each group) will be recruited. Although attrition in past similar work has been much lower, we estimate power under an assumption of 10% attrition (i.e., 180). Because pilot studies afford effect size estimates with wide confidence intervals due to small sample sizes, power analysis results were conducted for the effect size available from pilot data and lowest effect size that the after-attrition sample size affords. Feasibility of the expected effect size is then evaluated. Power analyses are based on primary variables (multi- and uni- sensory processing). If between-group differences occur on the putative covariates (i.e., pretreatment variables related to the outcomes) and they are associated with putative mediators or outcomes, the pretreatment variables will be statistically controlled after ensuring that the homogeneity of slopes assumption has been met. Pretreatment ERP variables will be statistically controlled regardless of the effect size of between-group differences to improve effect size estimates. Missing data will be handled using multiple imputation.

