## Protocol Title: Trial to Improve Multisensory Neural Processing, Language & Motor Outcomes in Preterm Infants

---

When the dependent variable is continuous, we will use ANOVAs when controlling for pretreatment variables and independent sample t-tests when there is no need for a covariate. When testing the nominal form of the sensory reactivity and adaptation outcome, we will use logistic regression.

*Statistical power:* Using PASS software, the estimated power using a 1-tailed test for an effect size based on the pilot data (Hedges  $g = .74$ ) with a sample size of 180 is over 99%. Even if the actual effect size is  $g = .35$ , we will have over 80% power to detect the effect under the proposed conditions. Detecting the required minimum effect size is probably for a number of reasons.

First, the expected effect size for the proposed treatment on multisensory processing should be larger than that derived from the pilot because the treatment used in the pilot

(i.e., skin-to-skin contact *without* the suck-contingent presentation of parent's voice) and theory strongly suggests the multisensory treatment will produce a larger effect than a unisensory treatment. Secondly, a medium main effect size of the proposed treatment on neurodevelopmental outcomes is expected because multisensory processing is moderately to strongly associated with later neurodevelopmental outcomes.

*Our second aim is to test the role of multisensory responses at discharge in mediating intervention effects on later sensory adaptation, and motor and language outcomes.*

Mediation models are presented in Figure 3. The indirect effect (the product of the a path coefficient \* the b path coefficient) will be tested for significance using the bias-corrected bootstrap method. The a path is the main effect of treatment on the ERP measure of multisensory processing. The b path is the association of the ERP measure of multisensory processing with the outcome controlling for the treatment group.

[figure not shown]

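### The list of pretreatment covariates contains two variables measured after randomisation, and the rule for selecting covariates tends to pick them when treatment has shifted them

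*Combined protocol and SAP*

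**What the plan says.** The Covariates paragraph in the Randomization section introduces a set of pretreatment covariates and fixes their timing: "These variables will be quantified at the pretreatment period". Its selection rule is that where "pretreatment variables showing between-group differences are associated with putative mediators or neurodevelopmental outcomes, these will be statistical controlled". The list then runs from gestational age, sex and brain injury to "cumulative caffeine exposure post intervention, total parental skin-to-skin time during the study period", and ends with pretreatment status on the General Movements Assessment (GMA).

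The analysis sections describe only baseline adjustment. Power/Sample Size says "the pretreatment variables will be statistically controlled after ensuring that the homogeneity of slopes assumption has been met". Statistical Analysis says "we will use ANOVAs when controlling for pretreatment variables". Pretreatment ERP is treated differently: Power/Sample Size controls it whatever the arm difference.

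On timing, Study design and setting randomises infants from 31 weeks. Study procedures starts the intervention at 32 0/7 weeks or at enrolment before 36 weeks.

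**The concern.** In a randomised trial, an arm difference on a true baseline variable is chance. On a variable that accrues after randomisation, a difference beyond chance is an effect of treatment. A rule that adjusts when the arms differ therefore tends to bring in such a variable when adjusting for it does harm. The interaction and homogeneity-of-slopes checks do not help, because a covariate moved by treatment can have parallel slopes.

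The route is plausible for parental skin-to-skin (STS) time. The Randomization section concedes that "we cannot fully mask parents to group allocation, as bedside nurses communicate regularly with them", so parents may behave differently by arm. Background and rationale reports from pilot work that "preterm infants exposed to STS care have increased multisensory processing efficiency compared to those who do not", which links STS to the construct used as the primary outcome. For caffeine the documents give no evidence either way.

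The Aim 1 comparison is at stake, as are the a-paths of Aims 2 and 3, which are treatment effects on ERP measures. The contradiction also leaves the primary model undetermined. One analyst could drop the two variables because they are not pretreatment, another could use them because they are listed, and both could claim to follow the plan.

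**Working it through.** **Timing.** Study-period STS time accrues after randomisation. Post-intervention cumulative caffeine could mean the total up to the end of the intervention or exposure after it; either reading includes time after randomisation. Neither fits the statement that the covariates are quantified before treatment.

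**Inputs from the plan.** The power section uses 180 infants (90 per arm), a minimum effect of 0.35 SD and a 1-tailed test.

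**Inputs assumed.** A 5% level for the one-sided test; two-sided p<0.05 for each part of the trigger (the plan gives no level); the treatment shift *s* in the covariate (in SD); and the within-arm correlation ρ between covariate and outcome.

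**Plan's own figure, as a reference point.** The unadjusted one-sided power at 0.35 SD is Φ(0.35 × √(90/2) − 1.645) = Φ(2.348 − 1.645) = Φ(0.703) = 0.759. The plan states over 80%. That is a separate matter and may reflect gain from the ERP covariate; 0.76 serves here only as the comparator.

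**How often the arm-difference test fires.** Power is Φ(|s| × √45 − 1.96). For |s| = 0.20, 0.35 and 0.50 this gives 0.27, 0.65 and 0.92, against 0.05 when s = 0.

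**Bias once adjusted.** Take M = M₀ + sT and Y = dT + ρM₀ + √(1−ρ²)·e, where T is allocation and d the total effect. Substituting M₀ = M − sT gives a coefficient on T of **d − ρs**. For d = 0.35, ρ = 0.4 and s = +0.5 this is 0.35 − 0.20 = 0.15; for s = −0.5 it is 0.55.

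**With the plan's rule.** The simulation (40,000 trials per cell) adjusts only if both the arm difference and the covariate–outcome correlation are significant, and otherwise uses the unadjusted t-test.

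| Shift s (SD) | Mean estimate, d = 0.35 (ρ = 0.2 / 0.3 / 0.4) | One-sided test result (same ρ) |
|---|---|---|
| 0 | 0.350 / 0.351 / 0.350 | power 0.76 unadjusted; type I error 0.05 |
| +0.3 | 0.309 / 0.285 / 0.263 | power 0.67 / 0.61 / 0.57 |
| +0.5 | 0.259 / 0.205 / 0.158 | power 0.53 / 0.40 / 0.30 |
| −0.3 | 0.380 / 0.411 / 0.436 | type I error (d = 0) 0.080 / 0.112 / 0.149 |
| −0.5 | 0.410 / 0.486 / 0.543 | type I error (d = 0) 0.137 / 0.250 / 0.385 |

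At d = 0.35 the full trigger fires in 4–5% of trials with no shift, 30–52% at |s| = 0.3 and 46–92% at |s| = 0.5.

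**A second mechanism.** Suppose the covariate has no effect on the outcome but shares an unmeasured cause with it (coefficient 0.45, assumed), and the true effect is zero. Shifts of +0.35 and +0.50 then give mean estimates of −0.09 and −0.15, with type I error 1.2% and 0.4%. Shifts of −0.35 and −0.50 give +0.09 and +0.15, with type I error 15% and 27%.

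**The case against.** The quoted conflict is not in dispute; its reach is.

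- **The inconsistency is narrow.** The rule, the power section and the analysis section all confine control to pretreatment variables, and only two list items break that. The list also directly follows a sentence on exploring whether treatment effects vary with these variables. This is fair, but the paragraph calls the whole set covariates, and a post-randomisation moderator has the same flaw.
- **No shift is shown.** The attrition paragraphs in the Randomization section call compensatory parental responses unlikely. The Multisensory Intervention section gives parental STS precedence over sessions, and STS is standard care in both arms. This stands: it limits what can be said about size and direction, and leaves caffeine without a named route.
- **Smaller shifts do less.** At 0.1–0.2 SD the mean estimate is about 0.31–0.39, power about 0.69–0.84, and type I error under negative shifts 5–8%. The 39% figure is the worst corner of the range. The same section implies parents are seldom present, so a normal covariate may model STS hours poorly. This also stands.
- **The simulation omits pretreatment ERP.** With ERP always adjusted (correlation 0.5 assumed), zero-shift power is about 0.85, so the power losses above do not forecast this trial. The bias was unchanged when ERP was added.
- **The trigger is harmless for true baseline variables.** The zero-shift results agree. Replacing it is justified by having a fixed primary model and is not needed to cure bias in those variables.

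**Conclusion.** The point holds. It is certain that the list contradicts the plan's own timing statement, and that nothing in the documents restricts these two variables to pre-randomisation values or to a sensitivity analysis. The bias is conditional: it needs treatment to shift the variable and the trigger to fire. If both happen, the estimate can be too small (treatment raises a helpful covariate) or too large (treatment lowers it), and the second case also inflates false positives. Under the assumed shifts of 0.3–0.5 SD and correlations of 0.2–0.4, an effect of 0.35 is estimated on average anywhere from 0.16 to 0.54; at 0.1–0.2 SD the distortion is at most about 0.04. These figures show the mechanism and do not predict this trial. It should be corrected before unblinded data are seen.

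A minor side issue is that pretreatment GMA status has no scheduled source. Study procedures says only that, before discharge, "a brief neurological examination (HNNE) and motor assessment (GMA) may be completed", which does not require it before the first session.

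**What to change.** 1. Remove post-intervention caffeine and study-period parental STS time from the adjustment set. Report both by arm, descriptively.
2. Replace the difference-triggered rule with a short prespecified list of variables measured before randomisation, for example gestational age, sex and pretreatment ERP (if recorded before allocation, otherwise before the first session). Adjust for them whatever the arm differences, as the plan already does for ERP.
3. If caffeine or STS is wanted as a covariate, use only the amount accrued before randomisation, and only if the medical record can supply it.
4. Use GMA as a covariate only where it was done before the first session.
5. Make the Covariates paragraph, Study procedures, Power/Sample Size and Statistical Analysis agree.

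The cost is a wording change. Extra chart abstraction arises only under item 3, because the Standard Care section describes STS monitoring without saying that pre-randomisation hours are extracted. No visit or treatment procedure changes.

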### **Intervention**

#### **Standard Care**

The standard care of infant currently follows two medical protocols, one for STS holding and one for exposure to parent's voice. The protocols will be enhanced and monitored as follows:

##### *Exposure to recorded parent's voice:*

Preterm infants in the NICU currently receive noncontingent recorded parents' voice during two 20 minute sessions per day. Recordings are standardized. Recordings are then played through a sterilizable device (DINO-egg).

To enhance standard care, we will ensure that all parents have a voice recording before study start when possible so that the majority of infants are exposed to parent's voice. A standard therapist recording may be used when it is not possible to obtain parent's voice. Monitoring of standard care will be accomplished through bedside logs, designed to be filled out by nursing staff and family when DINO-egg is played.

*Skin-to-skin holding:* Per standard care, STS care will be carried out by parents in both groups. Parents in the NICU currently use either their hands or positioners to facilitate prolonged STS. Infants are placed in a prone position with head positioned over the sternum, allowing transmission of breath and heart sounds to the developing ear. Deeper pressure is applied to offer support and feedback to the child's bottom. Session length is set to a minimum of 45 minutes per unit protocols. When primary caregivers are not comfortable with direct skin-to-skin contact (e.g. are not a direct relation to the child, or parent or child skin problem), a thin single-use hospital gown that is not previously imprinted with the parent's scent is used to facilitate the experience without hindering sound transmission. In order to ensure safety during STS holding, vital signs including heart rate, breathing patterns and rate, oxygen saturation and temperature are continuously and automatically monitored with preset alarms per unit protocol. If any negative deviation from the infant's daily vital patterns occurs, the nurses examine the infant and decide whether to stop the STS.

To monitor STS, we will review the medical record for daily start time, duration and caregiver during STS. We may also leave a STS log at bedside for parents who provide frequent STS to

## Protocol Title: Trial to Improve Multisensory Neural Processing, Language & Motor Outcomes in Preterm Infants

---

facilitate greater recording accuracy. We will also record any deviations from autonomic stability during STS (tachy/bradycardic events tachypnea or apnea).

### Multisensory Intervention

*Rational:* Studies have shown that infant acquisition of early speech sound differentiation in term and preterm infants is essential to the construction of more complex cortical functions such as receptive language development. Furthermore, learning of language in infants is improved when language exposure is presented contingent on infant action and promptly after the action. Therefore, we will use preterm infants' active non-nutritive sucking as the behavior that activates an audio recording of mother's voice within a one second after the suck. The mother's voice provides auditory input, which purportedly contributes to the infants' representation of initial speech sound categories.

The mother's voice is a preferred stimulus and its frequency and patterns are distinguished early in life from other sounds.

The infant must repeat the action every ten seconds to continue to receive the positive reinforcement of mother's voice. This approach enables contingent linguistic input by the infant's mother's voice without parent having to be present. Because infant uptake of linguistic input may be enhanced during periods of calm attention to the auditory stimulus, the contingent linguistic input will be provided while the infant is in a state of autonomic stability. Thus, we will present the suck-contingent playing of parents' voice while skin-to-skin (STS) holding occurs. STS holding is a form of MS stimulation combining tactile, vestibular, olfactory and auditory input that has been demonstrated to improve autonomic nervous system stability. Although STS can induce deep sleep, the contingent presentation of parent's voice will be provided at the beginning of STS containment, when past work indicates that infants are still awake.

*MS intervention protocol:* The MS intervention will be carried out in addition to standard care and will include two components: holding and light pressure containment of the infant against the cotton T-shirt covered chest of the therapist for tactile and non-specific auditory stimulation **simultaneous with** playing of mother's voice contingent on infant pacifier sucking for during a study session of no more than 15 minutes duration. No more than one study session will be completed per care period for each subject. Additionally, when possible, a 100% cotton T-shirt square scented with parent's skin may be placed within 2 cm of infant's face on the therapists' chest, to provide olfactory stimulation without risk of suffocation. The 12-23 intervention sessions will be dispersed across 2-3 weeks.

## Protocol Title: Trial to Improve Multisensory Neural Processing, Language & Motor Outcomes in Preterm Infants

---

On the rare occasion that the parent is present, parental STS will always take precedence over the intervention and the intervention session will be separated from previous parental STS by a minimum of 1 nursing care interval (3 hours) in one 24-hour period. Infant autonomic stability during the MS intervention with the therapist will be recorded as above for parent STS

*Contingent parent's voice exposure:* We will use the Pacifier Activated Lullaby® (PAL®) device, a 510k FDA approved digital music delivery system that integrates a sensor, a pacifier routinely used in the NICU, and a receiver). It delivers a predetermined 10 seconds of recorded parent's voice singing lullabies upon detection of a suck that meets a preset pressure threshold. The original systems were modified for research use by decreasing the lower limit of activation thresholds for delivering the recording. Minimal effort is required to trigger the device.

However, the settings ensure that regular attempts are needed to continue to receive continual presentation of the recording of mother's voice by requiring another suck after 10 seconds.

The auditory stimulation with PAL will be provided when the infants are still awake (i.e., at the beginning of the session).

*STS holding:* The therapist will wear a clean 100% cotton T-shirt with a clean hospital gown on top of the shirt (dependent on hospital guidelines) and wrap the "kangaroo" positioner securely over the gown. The positioner will allow containment with one-hand and PAL operations with the other. Should assistance be required, personnel will use the unit standard personal voice-activated call system to request a team member and minimize disruptions to the infant. The parent-scented T-shirt squares may be placed next to the infant's nose will be obtained by having the parent wear the T-shirt for a minimum of one hour and storing it in a sealed bag when possible. Once collected, the shirt will be cut into squares, and when possible, the first square will be used within 3 hours of cutting for the multisensory intervention. After each session the cloth will be stored in its own sealed bag and a new square will be used every 3 days. Each square will be replaced if contaminated with infant's bodily fluids.

*Relaxation training of the MS therapy team:* Because effects of STS holding are thought to be partly mediated by the holder's heart and respiratory rate, it is essential to maintain calm throughout the PAL administration in the way that parents would while holding their infant without additional activities. To promote this, therapists will be trained on mindfulness techniques and practice this prior to start of the intervention.

Ensuring high intervention fidelity:

The intervention will be implemented using a standardized training procedure implemented in the PI's lab for fidelity of parent training in a previous clinical trial. A script for the therapy session detailing the essential steps and sequence of the procedure is produced in a video. All

